### **5.6.1            Extent of Exposure**

Exposure to study drug information will be descriptively summarized by treatment as follows:

- Treatment duration (in weeks)
- Total number of administrations
- Total cumulative dose (mg)
- Number of dose-administrations at each dose level

### **5.6.2            Adverse Events**

All verbatim AEs terms will be coded using the Medical Dictionary for Regulatory Activities (MedDRA) version that is current at the time of the analysis (Version 25.0 or higher), and AE severity will be graded according to the scale defined in Table 5 in Section 5.3.3 of the study protocol (mild/moderate/severe). For each treatment group, the frequency of each AE preferred term will be defined as the number of participants experiencing at least one occurrence of the event. Each table will present the overall number and percentage of participants experiencing at least one AE and the total number of AEs reported. Percentages will be based on the number of participants in the safety-evaluable analysis set. In summary tables, AEs will be sorted by body system (in decreasing order of overall incidence), then by preferred term (in decreasing order of overall incidence). The summary tables will be restricted to treatment-emergent AEs, i.e., AEs that occur on or after the day of first dose of study drug. Non-treatment-emergent AEs (with onset before the first dose) will be listed.

The following safety information will be summarized by treatment group for the double-blind treatment period:

- AEs, AEs by intensity, AEs related to study drug
- Deaths
- SAEs, SAEs related to study drug
- AEs leading to discontinuation of study treatment

- AEs leading to dose modifications (dose interruption, dose reduction or delayed up-titration). Delayed up-titration at any given visit is defined as the simultaneous occurrence of the following two tick-boxes in the eCRF Adverse Events form:
  - Action take with Gantenerumab due to AE/SAE: Dose Not Changed
  - Was dose regimen modified from protocol schedule? Yes"
- Injection site reaction (ISR) signs and symptoms
- Systemic injection reactions (AEs with eCRF tickbox “systemic injection reaction” selected)
- ‘Hypersensitivity reactions’

Protocol-specified adverse events of special interest (AESI) will be listed.

The impact of the COVID-19 pandemic on the safety data will be assessed by reviewing the following:

- Confirmed or suspected COVID-19 AEs
- AEs associated with COVID-19
- Potential long COVID-19 symptoms

The following data handling rules will be applied for all AE summary tables:

- Events that are missing both at onset and at end dates will be considered to have started after the first dose of study drug and the duration will be set to missing.
- If the onset date is missing, and the end date is on or after the first dosing date or unresolved or missing, then the event will be considered to have started after the first dose of study drug.

The following data handling rules will also be applied for specific tables:

- An AE will be included in the summary table of AEs leading to study drug discontinuation if the “action taken with blinded gantenerumab” drop-down menu on the AE eCRF is checked “drug withdrawn”.
- In the summary table of AEs by intensity, if a participant has more than one occurrence of an event, the event with the most severe intensity will be counted. If the intensity of an AE is missing, then the AE will be included only in the total number of events column, and not in the count of participants with the event by intensity.
- In the summary table of AEs related to study drug, if a participant has more than one occurrence of an event, the related event will be counted if applicable. If the relationship of an AE is missing, then the AE will not be included.

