5.3.4 Assessment of Causality of Adverse Events

Investigators should use their knowledge of the participant, the circumstances surrounding the event, and an evaluation of any potential alternative causes to determine whether an adverse event is considered to be related to the study drug, indicating “yes” or “no” accordingly. The following guidance should be taken into consideration:

- Temporal relationship of event onset to the initiation of study drug
- Course of the event, with special consideration of the effects of dose reduction, discontinuation of study drug, or reintroduction of study drug (as applicable)
- Known association of the event with the study drug or with similar treatments
- Known association of the event with the disease under study
- Presence of risk factors in the participant or use of concomitant medications known to increase the occurrence of the event
- Presence of non-treatment-related factors that are known to be associated with the occurrence of the event

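### Adverse events with missing relationship are left out of the drug-related table, so the related count is a lower bound; count them as related and report how many by arm

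*SAP*

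**What the plan says.** SAP 5.6.2 plans summaries by treatment group that include AEs by intensity, AEs related to study drug, and "SAEs, SAEs related to study drug". It then gives two sets of data-handling rules.

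- **All AE tables, missing dates.** "Events that are missing both at onset and at end dates will be considered to have started after the first dose of study drug". An event that lacks only its onset date is handled the same way unless its end date falls before first dosing.
- **Specific tables, missing intensity.** "If the intensity of an AE is missing, then the AE will be included only in the total number of events column", and it leaves the participant counts by intensity.
- **Specific tables, missing relationship.** "If the relationship of an AE is missing, then the AE will not be included". For repeat occurrences in the same table, "if a participant has more than one occurrence of an event, the related event will be counted if applicable".

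The related-SAE table has no rule of its own. AE frequency is the number of participants with at least one occurrence, and "Percentages will be based on the number of participants in the safety-evaluable analysis set".

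Protocol 5.3 requires a causality assessment for each recorded AE. Protocol 5.3.4 has the investigator decide "whether an adverse event is considered to be related to the study drug", as yes or no. It does not say what to do with a blank. Neither document shows blanks in a separate row, counts them by arm or examines their effect.

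**The concern.** Causality is a two-valued judgment. In a table restricted to the yes answers, an omitted blank looks exactly like a no. The rule can therefore only leave the related count unchanged or lower it.

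Elsewhere the SAP resolves uncertain information the other way. Undated events are taken as treatment-emergent. A placebo participant who received any active dose is summarised as active (SAP Table 2). For the efficacy estimand, withdrawal from treatment without an informative reason is classed as related to drug or condition (SAP Table 3). No reason is given for handling missing AE causality differently.

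At stake is whether a reader of the related-AE and related-SAE tables can tell a complete count from a minimum. As planned, the tables give no sign of which it is.

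**Working it through.** **1. Figure to reproduce.** There is none. The SAP attaches no number to this rule, and neither document gives a rate of missing causality. The check compares the rules and then bounds the effect.

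**2. The three missing-data rules of SAP 5.6.2.**

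| Missing item | Applies to | Effect on the event | Still visible? |
|---|---|---|---|
| Onset and end dates | All AE tables | Counted as treatment-emergent | Yes |
| Intensity | By-intensity table | Out of participant counts by grade | Yes, in that table's total-events column |
| Relationship | Related-AE table | Out of the table | Not in that table; yes in the overall AE table |

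Only the relationship rule removes the event from its own table without trace.

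**3. Direction.** For one row of the related table in one arm, let:

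- N = participants in the denominator;
- R = participants with at least one occurrence recorded as related;
- k = participants with no occurrence recorded as related and at least one with relationship missing.

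Because a related occurrence is counted whenever there is one, a blank matters only for the k participants.

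- SAP rule: R/N
- Missing counted as related: (R + k)/N
- Difference: k/N, which is never negative and is zero when k = 0

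Taking the recorded judgments as given, R/N is the smallest possible value and (R + k)/N the largest.

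**4. Size in one arm.** N = 508, the planned number per arm (SAP 1.2); the actual denominator is the safety-evaluable set, which could differ slightly. The values of k are assumptions.

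| k (assumed) | k/508 |
|---|---|
| 0 | 0.00 points |
| 1 | 0.20 points |
| 5 | 0.98 points |
| 10 | 1.97 points |
| 25 | 4.92 points |

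**5. Effect on the difference between arms.** The change is (k active − k placebo)/508.

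- 5 and 5: (5 − 5)/508 = 0.00 points
- 5 and 0: (5 − 0)/508 = +0.98 points
- 0 and 5: (0 − 5)/508 = −0.98 points

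The absolute incidence moves in one direction only; the comparison can move either way or not at all.

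**The case against.** The strongest reply is that the rule will seldom bite and hides little when it does. Causality is a required yes/no for each AE. Discrepant entries are queried (Protocol 7.1) and source data are verified (Protocol 7.4). An excluded event stays in the overall AE table and in the serious, discontinuation and other tables where it qualifies. ARIA analyses rest mainly on MRI findings, and injection-site reactions are summarised separately. Safety analyses are descriptive, so no test or error rate depends on the rule. All of this stands and keeps the point minor. It limits the size of the effect but does not justify the direction of the rule.

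The documents do not support four stronger readings that a reader might infer:

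- **That the rule favours the drug against placebo, or undercounts more in the arm with more events.** It applies equally to both arms of a blinded trial, and no missing rate is given overall or by arm. Step 5 shows that the difference need not change.
- **That the date and relationship rules contradict each other.** They are in separate lists and do different work. Without the date rule, an undated event could drop out of every treatment-emergent table; a blank relationship costs the event only the related tables. The contrast is in caution, not in logic.
- **That the related count could rise by some 2% to 20%.** Dividing an assumed share of events with missing causality by an assumed share judged related gives 0.5%/30% = 1.7% up to 2%/10% = 20%. Neither share is in the documents. The ratio also counts events, while the SAP counts participants and lets a recorded related occurrence override a blank.
- **That missing intensity should be counted as severe.** This would put the top of three grades on an event with no supporting information, although the event is already kept in the total column. Showing it as missing is enough.

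**Conclusion.** The point holds, at low severity. The rule makes the related-AE count a lower bound. The related-SAE count is presumably affected in the same way, since it has no rule of its own. Nothing planned tells the reader how far below the upper bound either count lies.

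The shortfall is k/N per arm: zero if every relationship is recorded, and 0.98 percentage points for 5 affected participants of 508. That example rests on an assumed k and the planned arm size. The likely effect is small because the field is required. The conclusion concerns the absolute related incidence; it does not extend to a biased comparison between arms or to any hypothesis test.

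**What to change.** Before unblinding, change SAP 5.6.2 as follows:

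- In the related-AE and related-SAE tables, count an event with missing relationship as related. Apply this to repeat occurrences too, so that a participant with one unrelated and one blank occurrence is counted.
- Footnote each of these tables with the number so assigned, by arm, so that a reader can recover the count without the assignment.
- In the by-intensity table, add a missing row to the participant counts and assign no grade.

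The cost is a few sentences in the SAP and a minor programming change. If nothing is missing, the counts are unchanged. If something is missing, the related count becomes slightly less favourable and the reader can see why.

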### **5.6.3 Magnetic Resonance Imaging Safety Findings**

ARIA-E and ARIA-H are identified risks associated with gantenerumab. Sites were asked to capture all ARIAs as AEs in the eCRF that met any of the following criteria:

- Symptomatic ARIA-E (i.e., accompanied by CNS symptoms), and/or

- ARIA findings that result in a change in study treatment (e.g., dosage modification, treatment interruption, or treatment discontinuation), and/or
- Findings that are otherwise clinically significant in the investigator’s judgment

Not all ARIA MRI findings qualify as AE. ARIA analyses will be mainly based on ARIA MRI findings. ARIA AEs will also be reported. Based on MRI data, the incidence, and severity (based on the Barkhof Grand Total Score [BGTS]) ARIA-E and the incidence of ARIA-H will be summarized by treatment group and within this also by APOE ε4 genotype (by number of alleles) and by dose level. Additionally, the timing of ARIA-E and the timing to meet the protocol-defined criteria for permanent discontinuation due to ARIA-H will be also summarized by descriptive statistics and eventually by Kaplan-Meier methods. Recurrence of ARIA-E will be summarized by treatment group and within this also by APOE ε4 genotype (by number of alleles). ARIA-E associated with CNS symptoms (see Section 5.6.3.1) and with serious CNS symptoms will be summarized by treatment group and within this also by APOE ε4 genotype. Temporal co-occurrence of ARIA-E and ARIA-H will be summarized by treatment group and within this also by APOE ε4 genotype (by number of alleles). Temporal co-occurrence is defined as an MRI scan showing new ARIA-H that occurs between ARIA-E onset and resolution (inclusive), irrespective of the brain region.

MRI findings other than ARIA will also be summarized.

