1.2.2.1 Study NN19866

In the MAD study (NN19866), a total of 60 patients (34 males and 26 females) diagnosed with mild to moderate probable AD received multiple IV doses of gantenerumab (doses ranging from 6 mg to 20 mg, 60 mg, and 200 mg) or placebo every 4 weeks (Q4W) for up to 7 months. Owing to amyloid-related imaging abnormalities (ARIA), or ARIAs of “vasogenic edema” (ARIA-E) and of “hemosiderosis or microbleeds” (ARIA-H), on brain magnetic resonance imaging (MRI) scans that occurred in some patients after two to four doses of 200 mg of gantenerumab in Cohort 4 (200 mg IV Q4W gantenerumab [equivalent to 330 mg SC Q4W] or placebo), it was decided to terminate dosing for all patients on 9 June 2008. The findings resolved spontaneously within 1–4 months after discontinuation of gantenerumab and no patient required treatment.

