5.1.2 Management of Participants Who Experience Selected Adverse Events

Participants will undergo brain MRI examinations prior to every dose increase (pre-uptitration MRI scans) and according to the schedule of activities once the target dose is achieved. The pre-uptitration MRI scans will determine eligibility for the next uptitration dose. In the double-blind treatment period, a minimum of 3 doses of each dosing step have to be administered before the participant is eligible for the next uptitration dose. In the OLE, a minimum of 3 doses of each dosing step must be administered prior to be eligible for uptitration. In the OLE, a dose is defined as two consecutive dosing visits (one with an even dose number and one with an odd dose number, see [Table 4](#), Section [4.3.2.2](#)).

Participants will be eligible for uptitration if there are no new ARIA-E, if the ARIA-E is resolved (BGTS=0), and if the criteria for discontinuation because of ARIA-H have not been met.

In addition, the following dose adjustment and discontinuation rules for MRI findings will apply:

- In case of asymptomatic ARIA-E ≥ 1 and < 4 BGTS: Continue study drug at the same dose level (i.e., do not uptitrate) and repeat MRI 4 weeks later.

As long as BGTS is < 4 and ≥ 1 , continue study drug at the same dose level and continue MRI monitoring at 4-week intervals until the event resolves. When ARIA-E resolves, resume uptitration and MRI monitoring according to the schedule of activities.

If BGTS ≥ 4 or symptoms develop, refer to the rule below.

- In case of occurrence of symptoms in the presence of ARIA-E (any size) or asymptomatic ARIA-E with ≥ 4 BGTS: Temporarily interrupt study drug (but continue all assessments per schedule of activities) and implement MRI monitoring performed at 4-week intervals until symptoms and ARIA resolve.

When symptoms and ARIA-E resolve, reintroduce study drug at the next scheduled dosing visit, at the same dose given at the time the event was detected and perform an MRI scan after the first dose for participants on Q4W regimen and after the second dose for participants on the Q2W regimen.

If no new ARIA-E is detected, resume uptitration and obtain an MRI scan per the titration schedule. For participants on the Q2W regimen, perform another MRI scan 3 months after study drug reintroduction.

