5.3.5.1 ARIA Findings

Not every ARIA finding qualifies as an adverse event. An ARIA finding must be reported as an adverse event if it meets any of the following criteria:

- Symptomatic ARIA-E (i.e., accompanied by CNS symptoms), and/or
- ARIA findings that result in a change in study treatment (e.g., dosage modification, treatment interruption, or treatment discontinuation), and/or

- Findings that are otherwise clinically significant in the investigator's judgment.

Any accompanying symptoms should also be captured as separate adverse events.

It is the investigator's responsibility to review all ARIA findings.

Observations of the same clinically significant ARIA finding should only be recorded once on the Adverse Event eCRF (see Section 5.3.5.5 for details on recording persistent adverse events).

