Appendix 5 Amyloid-Related Imaging Abnormality Hazard Model (cont.)

**Table 4 Patient Population Included in ARIA-E Model Building
(Database as of 6 December 2016)**

Number of Patients (Number of Events)	Study WN25203	Study WN28745	Total	Comment
Total included in study	797 (63)	371 (35)	1168 (108)	
Placebo treatment	236 (2)	111 (3)	347 (5)	Excluded from model building
Total included in study on active drug	561 (61)	260 (32)	821 (103)	
Total on active drug before OLE, or treatment gaps > 70 days	125 (11)	108 (23)	333 (44)	Excluded from model building
Total included in model building	436 (50)	52 (9)	488 (59)	
Titrated without prior treatment	19 (1)	52 (9)	71 (10)	Included in model building
Constant dosing, and treatment gaps < 70 days	417 (49)	—	417 (49)	Included in model building

ARIA-E = amyloid-related imaging abnormality–edema/effusion; OLE = open-label extension.

As noted previously, the maximum likelihood estimation was performed using NONMEM software. Estimated model parameters were E_{max} , EC_{50} and the baseline risk for carriers and non-carriers. ARIA-E events were observation interval censored.

Parameter estimates are shown in [Table 5](#).

[figure not shown]
Table 5 ARIA-E Parameters for Gantenerumab When Applied to Titration Data

I_{BS}	ET_{50} (day)	γ	E_{max}	EC_{50} ($\mu\text{g/mL}$)
$5.84 \pm 4.22 \text{ E-6}$ (non-carrier)	323.44 F	2.15 F	7.12 ± 1.03	5.16 ± 2.85
$11.9 \pm 7.30 \text{ E-6}$ (carrier)				

ARIA-E = amyloid-related imaging abnormality–edema/effusion; F = fixed.

Visual predictive checks were performed to assess model performance. As shown in [Figure 3](#), the overall model performance was acceptable. [Figure 4](#) presents a condition that was excluded from the model building. The apparent bias in the prediction might be attributable to a SCarlet RoAD study effect, which will be followed up during ongoing completion of the database.

[figure not shown]
Figure 3 Visual Predictive Check on Database Used for Model Building

ARIA-E = amyloid-related imaging abnormality–edema/effusion.

Notes: Kaplan-Meier curves of the data are shown in green (dashed lines: 90% CI). Simulated study data (100 replicated Kaplan-Meier curves) are shown in blue with their mean and 90% CI. Inserted are the number of model-predicted ARIA-E events at given percentiles (2.5%, 50% [median], and 97.5%) and the actual observed number of events.

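### ARIA-E incidence by dose level has no exposure denominator, and scan gaps of 16 and 28 weeks after Week 60 blur the late timing summary

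*SAP*

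**What the plan says.** SAP 5.6.3 bases the ARIA analyses mainly on MRI findings. ARIA-E incidence and severity, and ARIA-H incidence, "will be summarized by treatment group and within this also by APOE ε4 genotype (by number of alleles) and by dose level". It adds that "the timing of ARIA-E and the timing to meet the protocol-defined criteria for permanent discontinuation due to ARIA-H will be also summarized". The methods named are descriptive statistics and possibly Kaplan-Meier. The section gives no person-time or scan-count denominator, no rule for dating onset and no interval-censored method. It does not say whether 510 mg Q4W and 510 mg Q2W are one dose level or two; output layouts are left to separate Data Analysis Plan modules.

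On scanning, Protocol 5.1.2 states: "Participants will undergo brain MRI examinations prior to every dose increase (pre-uptitration MRI scans) and according to the schedule of activities"; the second part of that rule covers the period after titration. Protocol Appendix 1, Tables 1 to 3, places the scheduled post-baseline scans at Weeks 12, 24, 36, 48, 60, 76, 104 and 116. SAP 5.3.2 gives 80 weeks at target dose.

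In the sponsor's own hazard model (Protocol Appendix 5, Section 3.1), "ARIA-E events were observation interval censored". A figure note in Section 3.2 of that appendix puts an early Kaplan-Meier mismatch down to the absence of scans in the first 12 weeks.

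**The concern.** A proportion of participants with ARIA-E at each dose level mixes risk with time under observation. One level is watched for 80 weeks and the others for 12, so the crude column need not order the levels as their event rates do. A reader will nevertheless take it as a statement about dose and risk.

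Timing has a smaller, related problem. A finding dated at detection is dated later when the preceding gap is 28 weeks than when it is 12, and an asymptomatic episode that appears and clears between two clean scans is never counted. Both effects concentrate in Weeks 60–104. The timing of ARIA-E is a listed safety endpoint (SAP Table 1), so these summaries will be read closely even though nothing is tested.

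**Working it through.** **Schedule.** The gaps between scheduled scans are 12, 12, 12, 12, 12, 16, 28 and 12 weeks. The 120 mg, 255 mg and 510 mg Q4W steps each have 12 weeks and one scan (Weeks 12, 24, 36). The 510 mg Q2W level has 80 weeks and five scans (Weeks 48, 60, 76, 104, 116). Participants who finished at Week 104 before the extension have less.

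**Reproducing the plan's figure.** Protocol 1.3.2 predicts an overall ARIA-E rate of about 26%.
- Concentrations c(t): two-compartment model, Protocol Appendix 4 Table 1 (CL 0.336, V2 3.52, Q 0.869, V3 6.38, ka 0.22, F 0.494), first-order absorption, trial doses × 1.18 for the G3-to-G4 exposure factor.
- Hazard: h(t) = I_BS × exp[ Emax·c/(c+EC50) × ET50^γ/(ET50^γ + t^γ) ], Protocol Appendix 5 Table 9 (I_BS 2.14E-5 non-carriers and 3.52E-5 carriers, Emax 5.92, EC50 6.78, ET50 323.44 days, γ 2.15). The appendix prints I_BS as an additive term on the log scale, but the tabulated values only make sense as hazards, so they are used that way.
- Result at Week 104: 19.2% in non-carriers and 29.6% in carriers. With two-thirds carriers (assumed; no share is given) this is 26.2%, and 24.4% to 26.5% for 50% to 70% carriers. The stated figure reproduces.

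**Dose level, same model, two-thirds carriers.** Rate = first events ÷ person-years at risk, with person-years ending at the first event.

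| Level | Weeks | Scans | First events, % of all | Person-years at risk per participant | Per 100 person-years |
|---|---|---|---|---|---|
| 120 mg Q4W | 12 | 1 | 3.70 | 0.226 | 16 |
| 255 mg Q4W | 12 | 1 | 7.74 | 0.212 | 37 |
| 510 mg Q4W | 12 | 1 | 6.59 | 0.195 | 34 |
| 510 mg Q2W | 80 | 5 | 8.51 | 1.162 | 7 |

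The target dose goes from highest to lowest. With those still event-free at entry to each level as denominator, the crude column becomes 3.7%, 7.74/0.963 = 8.0%, 6.59/0.8855 = 7.4% and 8.51/0.8196 = 10.4%, in the same order. Without stopping time at the first event, the rates are 16, 34, 29 and 5.6. The reversal also holds at 50% and 70% carriers and without the 1.18 factor.

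**Scan gaps.** If an episode is visible for D weeks and onset is uniform within a gap of G weeks, it is seen with probability min(1, D/G). With a flat true hazard, the detected rate in Weeks 60–104 relative to Weeks 0–60 is:
- D ≤ 12: [(16·D/16 + 28·D/28)/44] ÷ (D/12) = 24/44 = 0.55
- D = 17: [(16 + 17)/44] ÷ 1 = 33/44 = 0.75
- D ≥ 28: 1.00

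For findings that are detected, the average dating delay is half the gap: 14 weeks in a 28-week gap against 6 in a 12-week gap.

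**Compared with the real decline.** In the sponsor's model, onset per 12 weeks falls from 7.74% (Weeks 12–24) to 1.27 × 12/28 = 0.54% (Weeks 76–104), about 14-fold before any loss. With onsets placed within gaps as the model has them, the detected fall is about 26-fold at D = 17.4 weeks and 35- to 38-fold at D = 4.35 to 8.7 weeks. The schedule therefore enlarges the fall by a factor of about 1.8 to 2.6.

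**The case against.** Much of the case on the other side stands.

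- **The decline is real.** Protocol 1.2.3 reports that new ARIA-E in Study WN25203 peaked at 3 to 6 months and fell after the first year, and the hazard model contains a term that suppresses risk with time. A reader might infer from the schedule that the late fall is an artefact. The documents do not support that.
- **Duration is not known.** The only figure is "The findings resolved spontaneously within 1–4 months after discontinuation of gantenerumab", which is time to clearance after stopping drug in an earlier IV study. It is not time visible on continued dosing. At 28 weeks or more nothing is lost, and symptomatic episodes may prompt an unscheduled scan (Protocol 4.5.9).
- **Interval censoring does not recover missed episodes.** An episode between two clean scans leaves both clean. The method corrects onset dating only, and Appendix 5 has the same limit.
- **The ratio of exposure is not the size of the distortion.** A reader might infer a 5-fold (scans) or 6.7-fold (80/12 weeks) inflation at target dose. That needs equal hazard at every level, contrary to Appendix 5. Under the model the crude ratio is 8.51/7.74 = 1.1 to 8.51/3.70 = 2.3.
- **Exposure is reported elsewhere.** SAP 5.6.1 gives treatment duration and the number of administrations at each dose level, but it does not connect these to ARIA-E.
- **These are descriptive summaries, and both arms share the scheduled scans.** The randomised comparison of incidence is not biased in this way.

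One reservation about the ranking: 8.5% counts onsets. If detection loss is also applied with episodes visible for only 8.7 weeks, 510 mg Q2W shows 4.85% and comes second to 255 mg at 5.27%. It remains lowest per unit time. Because the model was fitted to detected events, that adjustment may double count.

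**Conclusion.** The dose-level limb holds and is the main one. As planned, the table would place the target dose at or near the top, while its event rate per unit time is about one fifth of that at the two preceding steps (7 against 37 and 34 per 100 person-years). This rests on the sponsor's model, the 1.18 exposure factor and an assumed two-thirds carrier share; the reversal is not sensitive to the last two.

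The timing limb holds in a limited form. Wider gaps in Weeks 60–104 delay dating and may lower detection to between 0.55 and 1.00 of the early level under a flat hazard, depending on an unknown duration. They exaggerate the late decline and do not create it.

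Three further readings are not supported. Nothing in the documents says that these curves will be used to relax monitoring. The low rate per unit time does not show that 510 mg Q2W is intrinsically safer, because dose level and time since first dose move together under forced titration. Nor does the text establish that the two 510 mg regimens will be pooled; it leaves the matter open.

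**What to change.** Amend SAP 5.6.3 as follows.

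1. Report dose-level ARIA-E as first events per participant-time at risk at that level, alongside the number of scheduled scans, with 510 mg Q4W and 510 mg Q2W shown separately. Note that dose level is confounded with time since first dose.
2. For timing, treat first ARIA-E as interval censored between the last clear scan and the first positive scan, as in Protocol Appendix 5. State that this corrects onset dating only.
3. State that the Weeks 60–104 rate is a lower bound, because episodes that start and clear between scans cannot be recovered. Compare rates over time only across periods with 12-week gaps (Weeks 0–60 and 104–116).

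The scan and dosing dates are already collected. The cost is a few extra table columns, some SAP wording and a slightly less favourable statement about the late period.
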